For the control group, all participants will receive minimal intervention with a one-page online information about procedures and tips of condom use. The site for control group will have similar graphic design as that for intervention group. However, there will be no self-assessment materials or online quiz questions. The time spent on the web information will approximately be 30 minutes for intervention group and 10 minutes for control group.

It is hypothesized that female students in the intervention group will have consistent condom use at 3- and 6-month follow-up compared to students in the control group. It is expected that the intervention will provide participants with increased knowledge,

attitude, norms, self-efficacy towards condom use, sexual consent and sexual coercion.

Measurements

The following measurements will be conducted at 3 time points: baseline (T1); 3-month post intervention (T2); and 6-month post intervention (T3), which consist of the same set of measurements. The individual characteristics will also be assessed at T1 and questions related to feasibility of the programme will be asked only at T3.

Primary outcomes

1. Change from Consistency in condom use with every partner: It will be assessed by using percentage of male condom protected sex with every partner according to the recommended guidelines from the systematic review of 56 studies.[22] Other behavioural items will also be asked, for examples, condom use at last sex and description of sexual partners (dating partner vs casual partner) at last sex.

Secondary outcomes:

- 2. Knowledge, attitude, norms and self-efficacy of condom use:** It will be assessed by 25-item MCAS[23] which contains assessment on five subscales: reliability and effectiveness of condoms, sexual pleasure associated with condom use, stigma associated with people proposing or using condoms, embarrassment about negotiating and using of condoms, and embarrassment about purchasing condoms. The measurement can be used with participants who do and do not have personal experience with condoms. The items are answered by a 7-point Likert-scale and total scores are ranged from 7 to 175. The higher the score, the more positive is the knowledge, attitude, norms, and self-efficacy of condom use.

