Participants will be asked to complete the web-based baseline survey at enrolment. The *web-based questionnaire* will be set up under an online platform. Participants may use their mobile devices including laptop computers and smartphones to complete the questionnaire. Participation is entirely voluntary. Written informed consent will be obtained via the web-based platform before completing the baseline questionnaire.

After completion of the questionnaire, the recruited students will then be randomized to either intervention group or control group, according to a list prepared by blocked randomization of a size decided by a *randomizer*. The block size and order of allocation will be kept securely in the randomizer to avoid selection bias. Allocation concealment will be done at the online platform according to the participants' enrolment sequence. The participant will then be guided to a web-page according to their group allocation.

At 3-month and 6-month after the entry of the study, participants will receive a link through their e-mail to complete a follow-up questionnaire (T2). Three months later, another e-mail link will be sent to participants for completing the last follow-up questionnaire (T3). If no response from a participant, a follow up telephone text-message and/or telephone call will be sent after 1 week as a reminder.

6. Treatment of Subjects

Not applicable

7. Assessment of Efficacy

Not applicable

8. Assessment of Safety

There is no question designed to provoke a strong or emotional reaction. If the participants find the intervention stressful or discomfort or having anxious physiological responses (for example, trembling, shaking, sweating, facial flushing, severe headache, shortness of breath, palpitations, severe pain or crying uncontrollably), they will be given the opportunity to decide whether to continue or to terminate the intervention and withdraw from the study.

9. Statistics

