To assess the efficacy of ICBI in increasing consistency of condom use, a linear mixed effects model will be adopted with intervention group and baseline consistency of condom use as the covariates. The group by time interaction shall be assessed for changes of ICBI effects over time. The mixed effects model was to take account of the extra covariance of repeated measurements at 3 and 6 months. The intention-to-treat principle will be adopted and all study subjects will be included in the analysis. Missing values at 3- and 6-month follow-up will be replaced by the last observed value and multiple imputation. The analysis will be repeated on the per-protocol set comprising individuals without missing values.

For secondary outcomes that were assessed approximately on a continuous scale, the same analysis approach as mentioned above will be adopted. For those assessed on a dichotomous scale, e.g. sexual coercion, similar approach by a non-linear mixed effects model with a logit link will be used.

The analysis will be performed by using the IBM SPSS (IBM Corp, Armonk, NY, USA). Each estimated effect will be accompanied by a 95% confidence interval and 5% level of significance.

10. Direct Access to Source Data/ Documents

The investigators and the research assistants of the research team are responsible for data collection and they will be permitted to access to source data and study record.

11. Quality Control and Quality Assurance

Daily logs will be recorded by the research assistants to monitor the study progress including the number of respondents approached, interviews completed or refused and incomplete interviews. All data entered in the database will be verified and cleaned. After completion of data entry, computer logic checks will be run for consistency of related code. Necessary corrections will be made to the database.

12. Ethics

The protocol will be submitted to the Institutional Review Board of the University of Hong Kong/ Hospital Authority Hong Kong West Cluster for approval. The conduct of the study will be complied to the “Declaration of Helsinki”. Participation in the study is voluntary. An information sheet is provided and a written consent is required from the participant for each individual study.

13. Data Handling and Record Keeping

The completed questionnaires and records will be kept by the Principal Investigator for 10 years. The computerized data will be kept for planning of future studies.

14. Financing and Insurance

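### Section 9 fills missing 3- and 6-month values by both last observation carried forward and multiple imputation, with no primary method; for early dropouts the carried value is the pre-intervention baseline

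*Combined protocol and SAP*

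**What the plan says.** Section 9 (Statistics) sets the primary analysis of condom-use consistency: "a linear mixed effects model will be adopted with intervention group and baseline consistency of condom use as the covariates". It adds: "The group by time interaction shall be assessed for changes of ICBI effects over time". On the analysis set: "The intention-to-treat principle will be adopted and all study subjects will be included in the analysis". On missing data: "Missing values at 3- and 6-month follow-up will be replaced by the last observed value and multiple imputation". The only further analysis bearing on missing data is this: "The analysis will be repeated on the per-protocol set comprising individuals without missing values". Continuous secondary outcomes follow the same approach, and dichotomous ones a similar one.

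Section 5 (Measurements) schedules assessments at baseline, 3 months and 6 months, with nothing in between. Section 5 (Procedures) places the baseline questionnaire before allocation: "After completion of the questionnaire, the recruited students will then be randomized to either intervention group or control group". Follow-up is by e-mailed link, with the same chasing in both arms: "If no response from a participant, a follow up telephone text-message and/or telephone call will be sent after 1 week as a reminder".

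**The concern.** The two methods rest on different assumptions and generally give different answers. The document does not rank them, call either one a sensitivity analysis, or give an imputation model or a number of imputations. If both are run, the trial has two primary results and no rule for which one counts.

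LOCF also has a specific weakness in this design. Before 3 months the only value available is the pre-randomisation baseline, which is also the model covariate. A woman lost before 3 months is recorded as unchanged at both follow-ups, whichever arm she is in. Every woman who leaves permanently, early or late, is recorded as unchanged between 3 and 6 months, and that feeds directly into the planned group-by-time interaction. The completers-only repeat does not protect against dropout that depends on the unseen outcome.

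**Working it through.** The plan gives no dropout rate, SD, effect size or power, so there is no figure of its own to reproduce.

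**Inputs.** From the plan: 500 women (section 5); 5% level and 95% intervals (section 9). Assumed: 250 per arm; SD 35 percentage points; correlations 0.6 (baseline with 3 months), 0.6 (baseline with 6 months) and 0.7 (3 with 6 months); 70% of dropouts lost before 3 months; dropout permanent and, unless stated, unrelated to outcome.

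**Closed form.** Let e and l be the shares lost before and after 3 months (I = ICBI, C = control), D3 and D6 the mean change without the intervention (drift), and E3 and E6 the true effects. An early dropout in the ICBI arm is given 0 instead of D6 + E6. A late one is given D3 + E3 instead of D6 + E6. Subtracting the same terms for control gives the bias of the 6-month LOCF estimate:

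bias = −eI × E6 − lI × (E6 − E3) − (eI − eC) × D6 − (lI − lC) × (D6 − D3)

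Simulation (20,000 trials per scenario; multiple imputation by arm with 20 imputations on 3,000 trials) gave the coverage and power figures below. Power is shown as LOCF / likelihood mixed model / multiple imputation.

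**Equal dropout, effect 8 at both visits, no drift.** The bias reduces to −e × 8.

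| Dropout | e | Formula | Simulated LOCF | LOCF coverage | Power |
|---|---|---|---|---|---|
| 5% | 0.035 | 8 − 0.28 = 7.72 | 7.7 | 94.6% | 88 / 88 / 88% |
| 10% | 0.07 | 8 − 0.56 = 7.44 | 7.4 | 94.1% | 86 / 86 / 86% |
| 20% | 0.14 | 8 − 1.12 = 6.88 | 6.89 | 92.5% | 83 / 82 / 82% |
| 30% | 0.21 | 8 − 1.68 = 6.32 | 6.34 | 88.7% | 79 / 78 / 76% |

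If 50% or 90% of dropouts leave early, the estimate is 7.2 or 6.6 at 20% dropout, and 6.8 or 5.8 at 30%. The average over both visits shrinks by the same amount (6.9 and 6.3; coverage 91.8% and 86.9%).

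**Unequal dropout, effect 8, drift the same at both visits.**

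| Control / ICBI dropout | Drift | Formula | LOCF coverage | Power |
|---|---|---|---|---|
| 15% / 25% | +5 | 8 − 0.175 × 8 − 0.07 × 5 = 6.25 | 88.6% | 74 / 82 / 81% |
| 15% / 25% | −5 | 8 − 1.40 + 0.35 = 6.95 | 92.8% | 84 / 83 / 82% |
| 15% / 30% | +8 | 8 − 0.21 × 8 − 0.105 × 8 = 5.48 | 82.0% | 63 / 81 / 80% |
| 15% / 30% | −8 | 8 − 1.68 + 0.84 = 7.16 | 93.5% | 86 / 81 / 81% |
| 30% / 15% | +8 | 8 − 0.84 + 0.84 = 8.00 | 95.1% | not tabulated |

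**No true effect.** Equal 20% dropout with drift 10 leaves the LOCF type I error at 5.0%, and 15%/25% with drift 5 gives 5.2%. At 15%/35% with drift 10 the bias is −0.14 × 10 = −1.40 and the error 9.2%. With drift 5 then 10 the bias is −1.40 − 0.06 × 5 = −1.70 and the error 11.3%.

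**Group-by-time interaction.** With p the total dropout, LOCF estimates (1 − pI) × (E6 − E3) − (pI − pC) × (D6 − D3). For an effect fading from 8 to 2 (true interaction −6, no drift, equal dropout) this is 0.8 × −6 = −4.8 at 20% dropout (coverage 91.4%) and 0.7 × −6 = −4.2 at 30% (85.1%). The 6-month LOCF effect itself stays near 2.

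A woman who misses 3 months but answers at 6 has baseline filled in at 3 months only. With a constant effect of 8, 10% permanent dropout, and 10% or 20% of the remainder missing only the 3-month visit, LOCF creates an interaction of 0.09 × 8 = 0.72 or 0.18 × 8 = 1.44 where none exists (type I error 5.8% or 9.1%).

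**Dropout related to baseline.** A separate 3-month simulation (4,000 trials, SD 35, correlation 0.5) used no effect, a change of 10 in both arms, and 30% ICBI and 15% control dropout, with women lower at baseline more likely to be lost. LOCF gave −2.9 with type I error 21%. A baseline-adjusted analysis of observed values held 5%.

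**Dropout related to unseen poor change.** With an assumed logit slope of 0.7 per SD, base rates 15%/35% and no effect, the type I error was 9.2% for LOCF, 15.8% for the mixed model, 15.8% for multiple imputation and 18.7% for completers.

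**The case against.** The sentence can be read as two separate analyses, both to be reported. Multiple imputation is then already planned, and the LOCF bias reaches the main result only if LOCF turns out to be primary, which the text does not say. This is fair, and it makes the missing ranking the certain defect and the bias a conditional one. Two reported analyses still need a stated order.

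The plan also takes steps to limit loss. Section 5 excludes women not willing to answer all three questionnaires, and both arms get the same reminders. Nothing points to unequal dropout. At 5–10% equal loss the harm is small, and the type I errors of 9–11% need strongly unequal loss together with drift, or outcome-related dropout. These points reduce the likely size but leave the rule unclear.

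Finally, LOCF is not worse throughout. Under equal dropout it loses no power and has slightly lower root mean squared error than the mixed model (2.60 v 2.76 at 20%; 2.84 v 2.95 at 30%). When dropout depended on unseen poor change, its type I error was lower than that of multiple imputation. This stands. It shows that the ranking depends on the dropout mechanism, and it is why a missing-at-random primary analysis needs a sensitivity analysis beside it. It does not justify a primary estimate that is biased even when dropout is unrelated to outcome.

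**Conclusion.** The concern holds and should be fixed. Two things follow from the text alone with high confidence: two imputation methods are specified without a primary, and carrying forward baseline gives a generally biased estimate if ICBI works and ICBI women are lost early. The exceptions are arm biases that cancel, lost women who truly did not change, and an effect that has faded by 6 months.

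The size is conditional on assumed inputs. Under equal dropout it runs from negligible at 5–10% to about one fifth of the effect at 30% (1.68 of 8), with coverage falling to 88.7% but no loss of power. Larger errors, in either direction, need unequal dropout with drift or dropout related to baseline. If multiple imputation is primary, this bias does not arise when dropout is unrelated to the unseen outcome. The open choice between two results remains until the plan closes it.

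**What to change.** In section 9:

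1. Name one missing-at-random method as primary. The smaller change is multiple imputation, done separately by arm, from baseline consistency, the baseline partner variables already collected (partner type at last sex, number of partners, relationship status) and whichever follow-up value is observed, so that women who miss only the 3-month visit are covered. State the number of imputations. A likelihood mixed model on observed values performs about as well, but it leaves out women with neither follow-up (500 × 0.20 × 0.70 = 70 at 20% dropout), whereas section 9 promises to include everyone.
2. Delete LOCF, or keep it only as a labelled secondary analysis.
3. Add a missing-not-at-random sensitivity analysis, for example delta-adjusted imputation with delta varied by arm.
4. Apply the same rule to the questionnaire outcomes measured at both follow-ups (items 2 to 5 of the outcome list), not to retention or website-usage measures.
5. Impute the primary percentage only where it is truly missing. Entry requires an intimate partner, not intercourse, so state how a percentage that is undefined because no intercourse took place will be handled.

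The cost is a few sentences and modest extra analysis, with no new data. Intervals will be wider than under LOCF: about 8% at 10% dropout, 17–18% at 20% (standard error 2.37 for LOCF, 2.78 for the mixed model, 2.80 for multiple imputation) and 29–31% at 30%.
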